## Aims/Hypothesis

The main question of the study is whether moderate-intense aerobic exercise, performed immediately following motor skill practice over a six-week intervention period, facilitates motor memory consolidation in Parkinson's Disease (PD).

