### Primary outcome measure

Description: Change of time in balance (mean angular displacement  $\pm 5^\circ$  from horizontal within each 30 seconds trial) from pre- to post-assessment.

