#### Memory consolidation (offline learning):

To assess motor skill consolidation (offline learning) primary and secondary outcomes will be calculated as change scores from the final performance (last practice block) of every practice session to the performance of the first practice block of the following practice session, respectively.

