## Study design

In an experimental trial, participants will be randomly allocated to one of two groups (Figure 1). Each experimental arm includes i) a pre-examination 2 - 14 days before ii) six acquisition sessions where the motor skill will be practiced, followed by a retention test iii) 7 days later (Figure 1). On acquisition days, the experimental group will perform a single bout of aerobic exercise (cycle ergometer) immediately following motor practice, whereas the control group will rest in a seated position.

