#### Motor skill practice:

Irrespective of group allocation, participants will follow the identical skill practice routine. On acquisition day, participants will perform a familiarization trial followed by 15 practice trials (30 seconds), clustered into 5 blocks of 3 trials, with 60 seconds rest between trials and 120 sec rest between blocks. At a baseline test 7 days prior to and at a retention test 7 days after the intervention period, participants will perform a test consisting of one familiarization trial (to account for potential warm-up effects) and one practice block (3 trials) on the stability platform, respectively.

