## Statistical analysis plan

**Power calculation:**

Considering data from previous experiments (Wanner et al., 2020), an a priori estimation of the required sample size for the primary analysis was performed using the statistics program G\*Power (version 3.1.9.4). The estimation was performed for the primary analysis, a 2 (groups) x 6 (training sessions) mixed ANOVA with repeated measures. In order to identify a significant interaction effect of moderate effect size ( $f=0.25$ ), with a statistical power of 80%, and a significance level of  $p\le.05$ , 20 subjects ( $n=10$  per group) need to be included.

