**Statistical analysis:**

The effect of aerobic exercise on motor skill learning will be examined by a 2 (groups) x 6 (sessions) mixed ANOVA with repeated measures, testing for the within-subject factor TIME (mean time in balance of all 15 trials in each of the 6 training sessions, respectively) and between-subject factor GROUP (AEX, REST). A separate 2 (AEX, REST) x 6 (last practice block during each training day, first block during subsequent session) ANOVA will be performed to test skill retention between practice sessions.

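### The primary analysis does not test the declared primary outcome: the 2 x 6 ANOVA of training sessions contains neither the baseline nor the retention test

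*Combined protocol and SAP*

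**What the plan says.** - **Declared outcome.** Under Primary outcome measure, the variable is time in balance and the contrast is change: "from horizontal within each 30 seconds trial) from pre- to post-assessment".
- **Assessments.** Motor skill practice schedules one familiarization trial and one block of 3 trials "At a baseline test 7 days prior to and at a retention test 7 days after the intervention period". Study design likewise has a pre-examination, then "six acquisition sessions where the motor skill will be practiced, followed by a retention test iii) 7 days later".
- **Primary analysis.** Power calculation states: "The estimation was performed for the primary analysis, a 2 (groups) x 6 (training sessions) mixed ANOVA with repeated measures". Statistical analysis defines the six levels as "mean time in balance of all 15 trials in each of the 6 training sessions, respectively".
- **Second analysis.** A separate ANOVA, not labelled primary, compares "last practice block during each training day, first block during subsequent session) ANOVA will be performed to test skill retention between practice sessions".
- **Main question.** Aims/Hypothesis asks whether aerobic exercise, "performed immediately following motor skill practice over a six-week intervention period, facilitates motor memory consolidation". Under Hypotheses, however, consolidation comes second, as the explanation for better learning.
- **Offline scoring.** Memory consolidation (offline learning) states that "primary and secondary outcomes will be calculated as change scores from the final performance (last practice block) of every practice session" to the first block of the next session.

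**The concern.** The outcome called primary and the analysis called primary are different quantities. The session ANOVA asks whether the two learning curves diverge during training. The declared outcome asks whether the groups differ in change from before training to after it. A trial that follows the plan would report a primary p-value for the first and no group comparison for the second.

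The two need not agree. Exercise comes after practice, so no session mean is measured after the sixth bout, and none after the 7-day interval that ends at the retention test. In a trial about consolidation, that is where an effect might be expected to show.

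With consolidation named as the main question, and offline scoring worded to include the primary outcome, three quantities could be presented as the primary result. The plan does not settle which, so the choice could be made after the data are seen.

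**Working it through.** **1. What enters the primary model** (trial counts from Motor skill practice; model from Statistical analysis)

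- Training trials: 6 sessions x 15 = 90 per participant, all used.
- Assessment trials: 3 baseline + 3 retention = 6 per participant, none used.
- Bouts completed before each session mean, exercise group: 0, 1, 2, 3, 4, 5.

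**2. Candidates for the primary result**

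| Quantity | Where it has primary standing | Planned group test |
|---|---|---|
| Pre-post change | Primary outcome measure | None |
| Six-session curve | Power calculation | 2 x 6 ANOVA |
| Offline change between sessions | Aims (main question); offline-scoring paragraph | Separate ANOVA, not labelled primary |

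**3. Which analysis the sample size belongs to**

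Inputs from Power calculation: f = 0.25, alpha 0.05, 80% power, 2 groups, m = 6 sessions, N = 20. The correlation between sessions and the sphericity correction are not stated; rho = 0.5 and epsilon = 1 are assumed.

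For the interaction, lambda = f² x N x m x epsilon / (1 - rho), with df1 = m - 1 and df2 = (N - 2)(m - 1).

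- N = 18: lambda = 0.0625 x 18 x 6 / 0.5 = 13.5; df 5 and 80; power 79.2%.
- N = 20: lambda = 0.0625 x 20 x 6 / 0.5 = 15.0; df 5 and 90; power 84.2%.

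So 20 is the smallest even total that reaches 80%, and the plan's figure reproduces for the session ANOVA. At N = 20 with rho = 0.3, 0.7 and 0.8, power is 68.2%, 97.8% and 99.9%.

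**4. What N = 20 gives for the pre-post change**

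The documents give no SD, no pre-post correlation and no pre-post effect, so only a range is possible. Three group differences in change were assumed, in SD units of a single assessment:

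- 1.46 SD, from f = 0.25 with a group gap that grows linearly. With session codes -2.5 to 2.5 the mean square is 2.917; the slope is 2 x 0.25 / sqrt(2.917) = 0.293 SD per session, and x 5 gives 1.46.
- 1.0 SD, from f = 0.25 with a single step after session 3 (2 x 0.25 = 0.5 SD either side of the mean gap).
- 0.75 SD, an assumed smaller effect.

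ANCOVA: noncentral t, df = N - 3 = 17, residual SD sqrt(1 - rho²). Change-score t test: df = N - 2 = 18, SD sqrt(2(1 - rho)). Both use 10 per group.

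| Power at N = 20 | rho 0.3 | 0.5 | 0.7 | 0.8 |
|---|---|---|---|---|
| ANCOVA, 0.75 SD | 38% | 45% | 60% | 75% |
| ANCOVA, 1.0 SD | 60% | 68% | 84% | 94% |
| ANCOVA, 1.46 SD | 90% | 95% | 99% | 99.9% |
| Change score, 0.75 SD | 27% | 36% | 54% | 71% |
| Change score, 1.0 SD | 43% | 56% | 78% | 92% |
| Change score, 1.46 SD | 74% | 87% | 98% | 99.8% |

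Difference detectable with 80% power at N = 20, same rho order: ANCOVA 1.27, 1.15, 0.95, 0.80 SD; change score 1.57, 1.33, 1.03, 0.84 SD.

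These figures do not show that the trial is underpowered. They show that the 80% claim does not carry over to the declared outcome.

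**The case against.** The strongest reply is that the firm conflict is between two quantities, not three. The offline-scoring paragraph opens by limiting itself to consolidation, and its reference to all outcomes cannot be literal, since MoCA and VO2max have no practice blocks. This partly stands: the pre-post change against the session curve is the core of the point. But the paragraph's wording does include the primary outcome, and the Aims make consolidation the main question, so the third reading remains open until the text excludes it.

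Second, post-assessment is never defined, and Figure 1 was not available for this check. Equating it with the retention test is an inference. It is supported by Secondary outcome measures, which uses the same pre/post wording for MoCA and other measures outside the practice routine. If pre and post instead meant sessions 1 and 6, an omnibus interaction with 5 numerator degrees of freedom would still not be a test of that change.

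Third, session 1 precedes all exercise, so the interaction does assess change from a pre-exercise value, and it fits hypothesis 1. That is true and makes it a reasonable analysis. It does not make it an analysis of the declared outcome.

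Fourth, the offline ANOVA has six levels, while six sessions give only five between-session intervals, so a sixth may end at the retention test. Even then it would compare the last training block with retention, not baseline with retention.

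Finally, the power range is wide and rests on assumptions. That is correct, and no claim of low power is made.

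**Conclusion.** The concern holds and must be fixed. As written, the primary analysis uses none of the 6 assessment trials, includes no value after the sixth exercise bout, and leaves the declared primary outcome without a group comparison. This follows from the text and rests on no numerical assumption; only the reading of pre- and post-assessment as the baseline and retention tests is inferred.

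The sample size of 20 is correct for the session ANOVA if rho = 0.5 and epsilon = 1. Whether it suffices for the pre-post change cannot be determined: ANCOVA power runs from 38% to 99.9% over assumed differences of 0.75 to 1.46 SD and correlations of 0.3 to 0.8.

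**What to change.** Before any comparison by group, reconcile Aims/Hypothesis, Primary outcome measure, Memory consolidation, Power calculation and Statistical analysis so that one outcome and one analysis are primary. The choice is the sponsor's.

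1. **Keep the declared outcome (preferred).** Primary analysis: ANCOVA of retention-test time in balance (mean of 3 trials) on group, adjusted for the baseline-test value, reporting the adjusted difference with its 95% CI. State that pre- and post-assessment mean these two tests. Keep the session ANOVA (hypothesis 1) and the offline ANOVA (hypothesis 2) as secondary, and amend the offline-scoring paragraph so that it no longer covers the primary outcome. A change-score comparison would also match; ANCOVA is preferred only for precision.
2. **Redefine the primary outcome as the six-session curve.** This keeps the basis for N = 20 but leaves the retention test and the sixth bout out of the primary comparison.
3. **Make consolidation primary.** Name the offline change and its ANOVA as primary, say whether a sixth interval ends at the retention test, and give a power calculation.

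**Cost.** Option 2 is wording only. Options 1 and 3 need no new visits or measurements for the analysis itself, since both tests are already scheduled, but each needs its own power statement. For option 1, f = 0.25 does not transfer directly, because a 3-trial mean has a different SD and reliability from a 15-trial mean. Insisting on 80% power could change the sample size: at rho = 0.5, ANCOVA needs N = 44 for 0.75 SD and N = 26 for 1.0 SD, while 1.46 SD already has 95% power at N = 20. If N stays at 20, the plan should state the power or detectable difference that results.
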